To address this gap in evidence, we will conduct the main randomized clinical trial (RCT) **ENRGISE (ENabling Reduction of low-Grade Inflammation in SENiors)** to test the ability of anti-inflammatory interventions for improving or preserving walking ability. We have maximized the public health impact of the interventions by selecting interventions that are safe, tolerable, acceptable, and affordable for vulnerable older persons. Based on an extensive literature review, we test the efficacy of the angiotensin receptor blocker (ARB) losartan (LO) and omega-3 polyunsaturated fatty acids (ω -3) as fish oil. To maximize the anti-inflammatory effect and potential benefit on mobility, we explore both individual and combination interventions that target different, but complementary and potentially synergistic anti-inflammatory mechanisms.¹²⁻¹⁵ We plan to recruit older persons at risk for, or with, mobility impairment, as measured by slow gait speed and self-reported mobility difficulty, and who have elevated blood levels of IL-6 (>2.5 pg/ml), the marker most consistently associated with mobility limitations.¹⁻⁷ Preliminary data on feasibility and information required for obtaining sample size estimates are needed to effectively design and implement the main trial. Thus, we implement the following **specific aims** for the ENRGISE Pilot Study:

- a. Conduct a pilot RCT in 300 older persons at risk of mobility decline to assess: (i) compared with placebo, the effects of LO, ω -3, and LO+ ω -3 on IL-6 and walking speed; (ii) the recruitment yields, the target population, adherence, retention, tolerability, sample-size, design, and cost for the main RCT; and (iii) the intra-subject variability of IL-6, and the dosage and safety of the interventions.
- b. Measure novel and established inflammatory markers to:
 - i. Characterize the effect of LO and ω -3 on these biomarkers and determine: (a) Are these cytokines/pathways impacted by the interventions? (b) Are the changes in these markers pre- vs. post-intervention less than, equivalent to, or greater than that of IL-6? and
 - ii. Assess if these biomarkers yield independent information from IL-6 with respect to change in walking speed and/or provide benefit for screening participants for the main trial.

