- The participant is diabetic and fasting glucose > 300 ,
- Baseline LDL > 130 AND increases by $\geq 20\%$ from baseline,
- The participant is taking a blood pressure lowering agent OR is also participating in the Losartan arm of the study AND blood pressure is $<90/50$, or
- Participant does not tolerate the fish oil.

The principal investigator/study physician at each site has the discretion to opt out of ω -3 fish oil dose adjustments due to glucose and/or LDL levels.

We increase the dose of ω -3 fish oil to 2.8 g/day if the average of IL-6 measured at 3- and 6-month visits has not **decreased by at least 40%** vs. baseline (average of screening visits 1 and 2). The 40% threshold is selected based on previous trials with ω -3 fatty acids. ω -3 fatty acids have been shown to reduce IL-6 by $>50\%$ in RCTs^{75, 76} and to be consistent with the threshold used below for losartan. To minimize the impact of outliers due to acute illness, the 3-month or the 6-month IL-6 measure are excluded or postponed if there is an acute illness within one month prior to the visit. In the rationale for dose titration we use the following assumptions:

1. IL-6 biovariation as a CV is $\sim 30\%$. This is a reasonable estimate based on our own estimates (unpublished data) and those of others.^{150, 151} This means that a SD of each person's day to day variability is about 30% of the mean value.
2. We have two measures at baseline that can be averaged to yield a reasonable estimate of each person's average value.
3. For dose adjustment we use IL-6 measured at 3 months and 6 months.
4. The half-life of IL-6 is extremely short (<30 minutes), so response to interventions is essentially coincident to the effect of the interventions.
5. We screen for outliers by excluding participants who experienced an acute illness within a month of the visit

6.2.b. LO and placebo (cellulose based) are obtained in 25 mg and 50 mg capsules. The shell capsules are cellulose based. Placebo and LO have identical shape, color, taste and weight. We start with 25 mg/day, if tolerated, we step up to 50 mg/day. If there are no safety concerns, we continue with 50 mg/day until the 6 month visit. If the average of IL-6 measured at 3- and 6-month visits does not **decrease by $\geq 40\%$** vs. baseline (average of screening visits 1 and 2), we increase the dose to 100 mg/day. Equivalent doses of ARBs have shown to reduce IL-6 by $>40\%$ ^{77, 78} and by 58% ⁷⁹ in RCTs.

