6.6. Recruitment – inclusion/ exclusion criteria - (details in Table 6.2.)

We identify men and women aged ≥ 70 years who are **able to complete the 400 m walk** at baseline, and are at **high risk of mobility disability** assessed by

- Self-reported difficulty walking ¼ mile or climbing a flight of stairs,
- Usual walking speed <1 m/sec and >0.44 m/sec on the 4 m walk (in the pilot phase we explore the feasibility of recruiting at least 50% of participants who have a baseline walking speed of <0.80 m/sec and >0.44 m/sec),^{22, 154, 155} and
- Chronic low-grade inflammation measured by IL-6 >2.5 pg/ml, the threshold we have found for increased risk of mobility limitation,^{1, 2} and <30 pg/ml to exclude high grade inflammation. To minimize within person variability,^{150, 156} IL-6 is the average of 2 measures taken at screening visits, with the first measure being >2.3 and <30 pg/ml, and the average of the two measures >2.5 and <30 pg/ml.

We exclude subjects with acute, autoimmune and HIV illnesses and causes of low walking speed that may be related to neurological conditions, severe arthritis, or low vitamin D. Other exclusion criteria reflect conditions that may interfere with the conduct of the study, interventions or assessments. Those taking ACEI or ARB are excluded from the LO randomization and those eating >2 servings/week of fish in the past year or taking fish oil are excluded from the ω -3 randomization. We recruit from the community. We use recruitment strategies successfully applied in LIFE,¹⁵⁷ LIFE-Pilot,¹⁵⁸ and TTrial,¹⁵⁹ which include primarily mass mailing, and newspaper, radio and TV ads and explore alternative recruitment strategies, such as electronic medical records to identify patients not taking study drugs and assess whether that strategy is effective in lieu of or in addition to mass mailing.

Table 6.2. Inclusion and exclusion criteria

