6.8. Screening, assessments and follow-up (Table 6.3.)

Potential participants are screened by telephone interviews to assess the main inclusion/exclusion criteria. Those who qualify are invited for the first screening visit during which a brief informed consent is obtained and the 4 m walk at usual pace is administered. Blood level of IL-6 is tested in those with a walking speed <1 m/sec and >0.44 m/sec. Participants with qualifying IL-6 levels are invited for the second screening visit to review medical history and current medications, complete blood testing (vitamin D, CBC, chemical panel, and second IL-6 measure), vital signs (blood pressure, pulse and temperature), 400 m walk, and the Mini Mental State Examination (MMSE).¹⁸⁵ The study medical safety officer will review the participant's health history, medication use, vital signs, and laboratory test results, and clear for randomization according to the study inclusion and exclusion criteria. If there are no safety concerns, participants attend the baseline visit during which the following is completed: full informed consent, questions to assess frailty,¹⁷¹ blood collection for labs, vital signs and anthropometric measurements, the SPPB, isokinetic dynamometry of the knee extensors and flexors, grip strength, and questionnaires. Validated Minnesota physical activity¹⁸⁶, depressive symptoms (CES-D)¹⁷⁵, patient reported outcomes (SF-36), and fatigability¹⁹⁸ questionnaires are completed at the baseline and 12 month visit. The physical activity results are used as potential modifiers in the data analyses. If there are no exclusion criteria identified, the participants are randomized, and the study drugs are dispensed. The baseline measures are repeated as outlined in Table 6.3. BP&P, blood tests and adverse events are measured about 1 week after randomization and after each visit when the LO dose is modified. Medication dose is adjusted as outlined in the above titration and safety algorithms.

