We use the "intention to treat" approach assuming participants are grouped according to randomization for all analyses of the intervention effect. The stratified recruitment and randomization allow us to compare mean log(IL-6) between each of the three active groups to placebo using a linear mixed model with both main effects and their interaction, adjusted for baseline log(IL-6) and strata. Time is a repeated factor, and the primary comparison is based on a contrast at 12 months. The covariance structure will be assumed to be unstructured. The primary focus is on marginal comparisons (135 and 165/group) between each active intervention and placebo using one-sided hypothesis tests at the 10% level (we are not looking for definitive evidence, but to rule out small effects). We assume 5% loss to follow-up (LTFU); this is similar to the 5% we achieved in LIFE. Using the root mean squared error from LIFE-P (adjusted for baseline log(IL-6) and treatment) of 0.52, we have 91% power to detect a difference if the difference (on the log scale) is at least 0.1625. This is equivalent to the difference between 4.20 and 3.57 pg/ml (or a 15% difference). We would have 66% power for a 10% difference (4.20 vs. 3.78 pg/ml, 0.1054 on the log scale) and 99% power for a 20% difference (4.20 vs. 3.36 pg/ml, 0.2231 on the log scale). Individual treatment group comparisons (at least 60 vs. 75/group) would have 44% power for a 10% difference, 68% power for a 15% difference, and 87% power for a 20% difference. This achieves the first part of Aim a (i). As sensitivity analyses, we also explore the impact of additional factors (e.g., diet, physical activity, medication use) by adding these factors to the models. Although the mixed model is robust against data missing at random (MAR), multiple imputation will be used in sensitivity analyses.

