To assess intra-person variability in IL-6 (Aim a (iii)), we measure IL-6 at both screening visits. We use a Bland-Altman plot to assess agreement; this is summarized using a 95% CI of the difference at the two visits providing information on the expected differences over one week due to biological variability and measurement error. If agreement is high, one measure is likely sufficient for recruitment into the main study. If not, we may need to use two or more measures to determine eligibility and to assess participant-specific risk.

6.10.d. Additional inflammatory biomarkers:

In addition to IL-6 levels, we examine additional markers of inflammation (Aim b (i) and (ii)). As with IL-6, our primary focus is on the relationships between changes in cytokines with the change in walking speed using linear mixed models. We use stratified linear mixed models (as described above for IL-6) to examine the impact of interventions on these cytokines. These analyses assess whether changes in these cytokines are of similar magnitude to IL-6. As the absolute levels differ between cytokines, focus is on relative changes from baseline. We also examine these cytokines in models also including baseline and follow-up log(IL-6) to assess whether they provide additional predictive information. We also explore MMD event rates by baseline levels of IL-6 and additional cytokines to explore whether we can use an additional cytokine to select a population at greater risk to use for the main study, recognizing the potential tradeoff between ease of recruitment and selecting a population at higher risk.

6.10.e. Informing the main study

We assess compliance and retention rates (Aim a (ii)). Although we expect to be underpowered for incident mobility disability, we collect these data and compare estimates of event rates to those obtained in SA group LIFE participants that would have been eligible for ENRGISE (Aim a (ii)). While power is limited, we also examine whether there is sub-additivity and interaction of interventions in stratum 3, which supports the decision of whether to proceed with a factorial or parallel group design in Phase 3 (Aim a (ii)). .

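### The two screening IL-6 draws are summarised by a 95% CI of the difference, which is an interval for the mean shift; 95% limits of agreement were probably meant

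*Combined protocol and SAP*

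**What the plan says.** Section 4, Aim a (iii), sets out to assess "the intra-subject variability of IL-6, and the dosage and safety of the interventions". Section 6.10.c serves the first part of that aim with the IL-6 values from the two screening visits. Agreement is judged on a Bland-Altman plot, and "this is summarized using a 95% CI of the difference at the two visits", this being described as "providing information on the expected differences over one week due to biological variability and measurement error". A planning decision follows: "If agreement is high, one measure is likely sufficient for recruitment into the main study"; otherwise two or more measures may be needed.

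Section 6.10.c does not give the scale of this comparison, and the documents nowhere mention limits of agreement or a criterion for high agreement. Elsewhere the plan treats IL-6 variation as proportional: the titration rationale in section 6.2.a.1 assumes that a person's "day to day variability is about 30% of the mean value", and section 6.10.b will "compare mean log(IL-6) between each of the three active groups to placebo".

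The pairs are selected. Section 6.6 requires two measures, "with the first measure being >2.3 and <30 pg/ml, and the average of the two measures >2.5 and <30 pg/ml", and section 6.8 says "Participants with qualifying IL-6 levels are invited for the second screening visit".

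**The concern.** The usual meaning of a 95% CI of a difference is an interval for the mean difference. Here it would answer whether IL-6 moved on average between the two visits. The aim, the stated purpose and the decision all ask something else: how much a single person's two values differ. The first interval shrinks with the square root of the number of pairs; the second does not depend on it.

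If the text is followed literally, the reported interval will look tight even when within-person variation is large. Someone planning the main trial who took it as the expected difference between two draws could conclude that agreement is high and that one measure is enough. The missing scale adds to this: if error is proportional to the level, no single interval in pg/ml fits everyone.

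**Working it through.** The plan gives no figure for this analysis, so there is none to reproduce.

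**Inputs**
- Within-person CV about 30% (section 6.2.a.1).
- IL-6 level 4.2 pg/ml, which section 6.10.b uses only to illustrate an effect size.
- 300 pairs, the randomised target (section 4). This is an assumption, because the number of people with two draws is not given.
- No mean shift for the basic comparison.

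**Original scale**
- SD of the difference = √2 × 0.30 × 4.2 = 1.78 pg/ml.
- 95% limits of agreement: ±1.96 × 1.78 = ±3.49 pg/ml.
- 95% CI of the mean difference: ±3.49/√300 = ±0.20 pg/ml.
- The limits are √300 = 17.3 times as wide as the CI. Under normality the CI would hold about 9% of individual differences: 2Φ(1.96/√300) − 1 = 0.09.
- With 600 pairs the CI falls to 3.49/√600 = ±0.14 pg/ml and the limits do not change.

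**The same CI can go with different agreement.** A half-width of 0.20 pg/ml at 4.2 pg/ml arises from each of these:

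| CV | Pairs | CI | Limits of agreement |
|---|---|---|---|
| 15% | 75 | ±0.20 | ±1.7 |
| 30% | 300 | ±0.20 | ±3.5 |
| 45% | 675 | ±0.20 | ±5.2 |

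**Log scale**
- Within-person log variance = ln(1 + 0.30²) = 0.0862. SD of the log difference = √(2 × 0.0862) = 0.415.
- Limits as a ratio: exp(±1.96 × 0.415) = 0.44 to 2.26.
- CI of the mean ratio: exp(±1.96 × 0.415/√300) = 0.95 to 1.05.

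**Why the scale matters.** At CV 30% the limits in pg/ml are ±1.96 × √2 × 0.30 × 2.5 = ±2.1 at a level of 2.5, and ±8.3 at a level of 10.

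**Effect of the first-draw gate.** Pairs were simulated with a true CV of 30% and kept only if the first draw was >2.3 and <30 pg/ml. Population medians of 2.5 to 4.2 pg/ml and between-person log SDs of 0.4 to 0.7 are assumptions. The upper limit of agreement came out at about 1.9 to 2.1 instead of 2.26, and the CV at about 28% to 29%. The mean difference turns negative through regression to the mean.

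**What the second draw buys at 2.5 pg/ml.** Misclassification at CV 30%, lognormal, for a person whose own level is 2.0 or 3.0 pg/ml, read as that person's median (or, in brackets, mean):

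| Level | One draw | Average of two, no gate | Plan's rule (first >2.3, average >2.5) |
|---|---|---|---|
| 2.0, wrongly in | 22% (18%) | 17% (12%) | 13% (9%) |
| 3.0, wrongly out | 27% (32%) | 17% (22%) | 26% (32%) |

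**The case against.** The best reply is that the method is right and only the label is loose. A Bland-Altman plot is named, the stated purpose describes limits of agreement, and the plot will show the scatter. The SD can be recovered from the CI as half-width × √n / 1.96. The team already assumes a CV of about 30% and averages two draws because of it, so it is unlikely to take ±0.2 pg/ml for within-person variation. No numerical rule is tied to the interval. All of this stands, and it limits the severity. It does not remove the mismatch: nothing elsewhere corrects the phrase, and a summary should not have to be inverted to answer its own question.

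Three stronger readings are tempting and should not be drawn.
- A reader might infer that the CI is uninformative or that a wrong main-trial decision will follow. The back-calculation, the plot and the absence of a numerical rule do not support that.
- A reader might infer that the second draw removes about 6 percentage points of misclassification at 2.0 pg/ml and 10 at 3.0. That holds only for an average of two draws with no gate. Under the rule in section 6.6 the gain over one draw is about 9 to 10 points at 2.0 and about 1 point or none at 3.0.
- A reader might take limits of agreement from these data as a clean estimate for the screened population. The gate shifts them.

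**Conclusion.** The point holds as a minor correction. As written, the named summary is an interval for the mean shift and does not directly address intra-person variability or the choice between one and two measures; limits of agreement were probably meant. The gap is ±0.20 against ±3.5 pg/ml, or ratios of 0.95 to 1.05 against 0.44 to 2.26. These sizes rest on the plan's CV, on everyone being at 4.2 pg/ml (for the pg/ml figures) and on 300 pairs; the factor √n between the two intervals depends only on the number of pairs. The gated figures rest on the assumed populations above. This is a planning analysis: efficacy analyses, pilot eligibility and titration are unaffected.

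**What to change.** In section 6.10.c, replace the phrase with 95% limits of agreement on log(IL-6), back-transformed to ratios, together with the within-person CV. Report the mean difference separately. Add that second draws are taken only after a first draw >2.3 and <30 pg/ml, so the mean difference, the limits and, slightly, the CV are affected by that selection.

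The cost is a sentence or two of wording; the data are already collected. Sampling error is no obstacle: at CV 30% and 300 pairs, the 95% CI of the CV is about 27.7% to 32.7% and that of the upper limit about 2.08 to 2.45 around 2.26 (SE on the log scale = 0.415 × √(1/300 + 1.96²/(2 × 299)) = 0.041). The selection shift in the upper limit is of similar size to that interval's half-width, which is why the caveat belongs in the text.

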6.2.a. ω-3 fish oil and placebo (corn oil) are obtained by Epax in 0.7 g gel caps and they have identical shape, color, taste and weight. Each 0.7 g of fish oil ω-3 contains 400 mg eicosapentaenoic acid (EPA) and 200 mg docosahexaenoic acid (DHA). We start with 1.4 g/day of fish oil and continue until the 6 month visit. If the average of IL-6 measured at 3- and 6-month visits does not **decrease by ≥40%** vs. baseline (average of screening visits 1 and 2), we increase the dose to 2.8 g/day. To limit the effect of within subject variation, we use the average of 2 measures. If there is an acute illness within one month prior to the visit, the 3-month or the 6-month IL-6 measure is postponed or excluded from titration algorithms. In previous RCTs, ω-3 reduced IL-6 by >50% using 1 to 2 g/day of fish oil.^{75, 76} In other trials in elders, fish oil was used in comparable doses

ranging from 0.6 to 2.3 g/day.⁶²

6.2.a.1. Risks and risk protection and dose adjustments related to administration of ω -3

There are no contraindications to the use of ω -3 fish oil, except intolerance or allergy to fish oil. ω -3 are considered very safe and produce only mild adverse effects involving gastrointestinal upset and fishy aftertaste.^{148, 149} FDA has affirming menhaden fish oil as **Generally Recognized As Safe (GRAS)** under 21 CFR 4 184.1472 provided that the daily intake of EPA and DHA combined do not exceed 3 g per person per day. <http://www.accessdata.fda.gov/scripts/cdrh/cfdocs/cfcfr/CFRSearch.cfm?fr=184.1472> and <http://www.fda.gov/Food/IngredientsPackagingLabeling/GRAS/SCOGS/default.htm> accessed on 9/11/2014.

ω -3 may rarely cause clinical or subclinical bleeding, worsening of glycemic control in people with impaired glucose tolerance, rise in LDL cholesterol, and possibly hypotension when combined with antihypertensive treatment.

We start with a dose of 1.4 g/day of ω -3 fish oil. Adverse effects, such as gastrointestinal discomfort are monitored. Dose will be adjusted as below based on serum glucose, LDL cholesterol and hemoglobin measured at baseline and at month 3, 6, and 9. ω -3 fish oil dose will be decreased or discontinued if any of the following criteria are met at follow-up:

- New onset paroxysmal or persistent atrial fibrillation
- Hemoglobin decreases by $\geq 20\%$ from baseline (dose will be discontinued),
- The participant is not diabetic and fasting glucose is > 126 AND has increased by $>30\%$ from baseline,

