Questionnaires				x								x		
Dispense study drugs				x		x		x		x				
Assess compliance						x		x		x		x		
Proxy interview (if needed)						x		x		x		x		

* BP, and serum potassium and eGFR are measured about 1 week after the LO dose adjustment (potassium and eGFR are not measured if LO dose is reduced only for BP values). ** Extra visits if there are safety concerns. & The IL-6 measure is excluded or postponed if there has been an acute illness within one month prior to the visit.

Participant Reported Outcomes (PRO).

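### The Aim b (ii) marker models adjust for follow-up IL-6 measured once per visit, so a marker that tracks IL-6 can look independent of it when it adds nothing beyond true IL-6

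*Combined protocol and SAP*

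**What the plan says.** Section 4, Aim b (ii), sets the question: "Assess if these biomarkers yield independent information from IL-6 with respect to change in walking speed and/or provide benefit for screening participants". Section 6.9 repeats it. Section 6.10.d gives the method, which is to put each marker into a walking-speed model that also holds IL-6: "We also examine these cytokines in models also including baseline and follow-up log(IL-6) to assess whether they provide additional predictive information".

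The protocol is open about the noise in IL-6. Among the titration assumptions in section 6.2.a.1 it states: "This means that a SD of each person's day to day variability is about 30% of the mean value". It averages two draws at baseline ("We have two measures at baseline that can be averaged to yield a reasonable estimate of each person's average value") and again for titration (section 6.2.a: "To limit the effect of within subject variation, we use the average of 2 measures"). Table 6.3 schedules one IL-6 measure at each of months 3, 6, 9 and 12. The table's footnote deals with acute illness ("The IL-6 measure is excluded or postponed if there has been an acute illness within one month prior to the visit"), which removes some outliers but not ordinary day-to-day variation.

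Section 6.10.d mentions neither averaging of follow-up IL-6 nor correction for its error. The paired screening draws serve eligibility, the baseline value, titration and a Bland-Altman plot (section 6.10.c). Section 6.10.d gives no marker list, marker correlations, test level or decision rule.

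**The concern.** Adjusting for a covariate measured with error removes only part of its effect. What remains of the true IL-6 effect sits in the residual, where any second measure of the same inflammation can absorb it. A positive marker coefficient then shows information beyond the IL-6 values recorded, which is weaker than information independent of IL-6.

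Aim b (ii) asks for the stronger statement, so the pilot could credit a redundant marker with a separate pathway. The bias does not shrink with sample size, and it is largest when the trial's own hypothesis is true, that is, when falling IL-6 goes with better walking speed.

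**Working it through.** **1. The plan's nearest figure.** Section 6.10.d states no operating characteristic. Section 6.10.c gives 80% and 90% power at correlations of -0.126 and -0.152 (n=285, one-sided 10%). By Fisher's z, Φ(atanh(0.126)·√282 − 1.2816) = Φ(0.846) = 80.1%, and for 0.152, Φ(1.291) = 90.2%. Both reproduce and are not in dispute.

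**2. Error variance.** A CV of 30% gives log variance ln(1 + 0.30²) = 0.0862 per draw (SD 0.294). The two-draw baseline mean has 0.0862/2 = 0.0431.

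**3. Reliability of the IL-6 change.** The inputs are the residual SD of 0.52 in section 6.10.b and an assumed true baseline variance on the log scale. The 0.52 is treated as if it came from this design.

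- Baseline variance 0.25: the residual baseline part is 0.25 × 0.0431/0.2931 = 0.0368. The true-change variance is 0.52² − 0.0862 − 0.0368 = 0.1474. The reliability of the simple change is 0.1474/(0.1474 + 0.0862 + 0.0431) = 0.53. Entered as two covariates, baseline and follow-up IL-6 explain 0.1474/0.2704 = 0.545 of the true change and leave 0.455.
- Baseline variance 0.16 with true-change variance 0.155: 0.155 + 0.0862 + 0.0340 = 0.275 (SD 0.525, close to 0.52). The share explained is 0.155/0.275 = 0.56, leaving 0.44.

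Baseline variances from 0.15 to 0.40 change the simple reliability little (0.54 to 0.53).

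**4. Closed-form check.** Let s be the unadjusted share, ρ the true correlation of IL-6 change with speed change, and m the correlation of the measured marker change with true IL-6 change. The marker is otherwise unrelated to speed. Its partial correlation with speed change is, in size,

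mρs / √[(1 − m²(1 − s))(1 − ρ²(1 − s))].

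An observed correlation of -0.126 corresponds to ρ = -0.126/√0.53 = -0.173. With s = 0.455:

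- m = 0.5: 0.0394/0.922 = 0.0427. The rejection rate is Φ(0.0427·√280 − 1.2816) = 29%.
- m = 0.7: 0.0551/0.849 = 0.0649. The rejection rate is 42%.

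Simulation of the same 12-month model gave 30% and 43%, against a nominal 10%. For weakly related markers (m = 0.1 to 0.2) it gave 13-15%.

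**5. Main figures.** These come from simulation with n=285 and a one-sided 10% test. Walking speed depends on true IL-6 change only. The marker's correlation with IL-6 is between true levels, and the marker has its own independent noise on top. Rates at 0.5 and 0.7 are therefore lower than in step 4, where m already includes that noise. The range covers ρ from -0.15 to -0.20.

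| Marker–IL-6 correlation | Redundant marker called independent |
|---|---|
| 0.3 | about 16% |
| 0.5 | 18–21% |
| 0.7 | 24–33% |
| 1.0 (perfect proxy) | 38–50% |

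With reliability 0.53 these ρ values mean observed correlations of -0.15 × √0.53 = -0.11 and -0.20 × √0.53 = -0.15, about the range for which section 6.10.c gives power. If ρ = 0 the rate is about 10% throughout.

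**6. Sensitivity.**

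- Two-sided 10% test, step 4 setting: 20% and 30% at m = 0.5 and 0.7.
- CV of 20% instead of 30%: 14%, 16% and 20% at m = 0.3, 0.5 and 0.7.
- Marker and IL-6 errors shared within a visit: the perfect-proxy rate at ρ = -0.20 falls from 50% to 37%.
- Repeated-measures version using months 3, 6 and 12, observed correlation -0.126: 27-75% at m = 0.5, depending on the assumed outcome ICC and the stability of the true change. Using several visits does not remove the problem.

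**7. After correction.** An errors-in-variables correction with known error variance gave 10.0-10.4% at m = 0.3 to 0.7 and 8-9% at 0.9. A check of the correction using the screening draws gave about 9-12%, with 12% when eligibility truncates those draws.

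**The case against.** The strongest reply is that section 6.10.d asks a predictive question. For prediction or screening, IL-6 as measured is the right comparator, and a marker that adds to it is useful whatever the reason. That stands, and the uncorrected model should be kept for that purpose. It does not cover the other half of the aim, "Assess if these biomarkers yield independent information from IL-6 with respect to change in walking speed", which is a statement about IL-6 itself.

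It also stands that the step is exploratory. The 10% level is stated for efficacy and is only assumed here. Choosing a population for the main trial is handled by a separate look at MMD event rates, and section 6.10.e does not name this model among the inputs to the main-trial decision. A false finding would mislead interpretation more than trigger a fixed rule.

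A reader might infer that any correlated marker will usually pass, or that error rates reach 67-81%. The documents do not support that. Those rates need a marker that is an exact proxy for IL-6 with no more noise than IL-6 has, and ρ = -0.30, which is an observed correlation of about -0.22 and beyond the values in section 6.10.c. Nor does adjustment leave most of the true IL-6 change behind: it leaves about 44-46%.

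**Conclusion.** The point holds as a limited, inexpensive improvement. As written, section 6.10.d cannot separate a marker that carries information beyond IL-6 from one that repeats it with different noise. For a redundant marker the false rate runs from about 16% (correlation 0.3) to 38-50% (perfect proxy), against an assumed 10%.

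This rests on the protocol's 30% CV and 0.52 residual SD, on ρ between -0.15 and -0.20, on independent errors, and on marker correlations that the documents do not supply. The rate is lower if errors are shared within a visit or the CV is smaller, and there is no inflation if IL-6 change is unrelated to walking-speed change. The uncorrected model remains sound as evidence of information beyond measured IL-6.

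**What to change.** In section 6.10.d, add an errors-in-variables or regression-calibration analysis of the marker models. Estimate the IL-6 error variance from the two screening draws, and note that the eligibility limits truncate those draws. Base any statement that a marker is independent of IL-6 on this analysis. Describe the uncorrected model as showing information beyond measured IL-6, and keep it for prediction and screening.

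Averaging IL-6 over follow-up visits is at most a partial sensitivity analysis. Doses may change after month 6, so the mean mixes treatment periods, and the additional markers are not measured at month 9. In the three-visit simulation with a stable true change, averaging lowered the rate at m = 0.5 only from 36% to 20% (outcome ICC 0.5) or from 27% to 14% (ICC 0.8). Benchmarking a marker against a second IL-6 draw is not possible, because no follow-up visit has two.

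The cost is SAP wording and some extra analysis of assays already planned. Intervals will be wider and fewer markers will be called independent.
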